4.4 Primary Study Endpoints

Change in Modified CAILS of index treatment lesion and index control lesion (week 0 and 4) and change in lesion count (week 0 and week 4).

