Lichenoid tissue reaction (LTR) includes: lichen planus (LP) cutaneous lupus, dermatomyositis (DM), and graft versus host disease (GVHD). The pathogenesis of LP is incompletely understood; however, it is clearly T-cell mediated without a known auto-antigen. Lichen Planus (LP) is an inflammatory skin condition characterized by purple, polygonal, pruritic, papules and plaques. LP can affect any ectodermally derived tissues including: the skin (most commonly), nails, and mucous membranes. LP is thought to affect approximately 1-2% of the general population. Most cutaneous LP resolves within one to two years. Disease duration, in ascending order, is: generalized cutaneous, non-generalized cutaneous, cutaneous and mucosal, mucosal, hypertrophic, and Lichen Planopilaris (hair LP). LP is the prototypical lichen tissue reaction(LTR). Modern theories of LP encompass three major stages: antigen recognition, lymphocyte activation, and keratinocyte apoptosis. A fourth stage, resolution, is a new and emerging topic. The occurrence of triggering factors in a genetically predisposed individual carrying LP-associated genes, results in disease development. During the initiation phase, damage to keratinocytes result in the release of DNA, RNA, and cathelicidin (LL37). These proteins can stimulate plasmacytoid dendritic cells (PDC) via toll like receptors 7, 9 (TLR7,9) which result in the release of interferon alpha (IFN α). IFN α can have both local and distant affects upon myeloid dendritic cells (MDC) as well as keratinocytes. Stimulated MDC interact with CD4+ T-helper cells and with the correct antigen. The antigen remains unknown but may represent a viral derived peptide. Signaling receptors on MDC will stimulate CD4+ T-helper cells via the release of Tumor necrosis factor alpha (TNF α), Interleukin-1 (IL-1), and -12. In addition, cluster of differentiation- (CD40) and CD40 ligand (CD40L) will result in the co-stimulation of the T-helper/MDC interaction. Stimulated CD4+ T-helper cells then release of interferon gamma (IFN γ) and IL-2. These cytokines stimulate CD8+ T-cytotoxic cells. The stimulated CD8+ cells expressing Chemokine receptor-3 (CXCR3) will migrate to the dermal-epidermal junction following the release of chemokines ligands 9(CXCL9), -10,-11. These chemokines are released by stressed and stimulated keratinocytes. The stimulated CD8+ cells will interact with the stressed keratinocytes and can induce apoptosis in with the proper and signaling receptors. This antigen also remains unknown but may be a self-antigen released by local stress. The major kill signals are TNF α , granzyme, and perforin. Fas and Fas ligand (FasL) are expressed on both keratinocytes and lymphocytes. Local CXCR3+ DC and T-regulatory cells may also modulate the local lichenoid response.

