INCB018424 taken systemically can inhibit the growth of blood cells. Low blood cells can make subjects more susceptible to infections by bacteria, virus, and fungi. The risk is low with systemic therapy and was not noted with topical therapy but subjects will be monitored for any signs of inhibition of their blood counts.

Infection risk:

There is a theoretical increase in risk of infection with topical use of INCB018424 PHOSPHATE CREAM. This will be monitored for.

INCB018424 may increase risk of infections and reactivation of latent infections such as Tuberculosis or Valley Fever. Serious bacterial, fungal and viral infections were observed in patients receiving INCB018424. Please seek medical advice if signs or symptoms suggestive of infection occur.

Allergy:

It is possible that some people could have an allergic reaction to INCB018424 PHOSPHATE CREAM.

Cancer Risk:

INCB018424 PHOSPHATE CREAM may have the potential to affect subject's immune system; they may be at increased risk for infections and possibly cancer. Live vaccines should not be given concurrently with INCB018424 PHOSPHATE CREAM.

Pregnancy Risk:

The effect of the study drug on a fetus (developing baby still in the womb), or on a breastfeeding infant, is unknown and may be harmful. Because of these risks, women cannot take part in this study if they are pregnant or breastfeeding.

Skin biopsy:

A skin biopsy is generally a safe procedure, but some potential risks may include local pain, mild local bruising, bleeding, scarring, and an infection at the site where the skin biopsy was performed. If a topical antibiotic is used afterwards, then there is a small risk of an allergic reaction.

Chest X-ray:

Subjects will be exposed to radiation from the chest x-ray. The amount of radiation has a low risk of harmful effects.

Blood draw:

The risks of drawing blood include pain, bruising, lightheadedness, and/or fainting, or rarely, infection at the site of the needle stick.

Other:

As with all research, there is a chance that confidentiality could be compromised; however, we take precautions to minimize this risk.

3 Study Objectives

Primary Objective:

To determine the efficacy of INCB018424 PHOSPHATE CREAM as measured by the change in Modified CAILS score of the index treatment and control lesion (weeks 0 and 4) and changes in lesion count (week 0 and 4)

Secondary Objective:

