4.1 General Description

This is a single center, exploratory, open-label, single-arm design study of 12 patients. Treatment naïve and treatment refractory patients with LP will be treated with INCB018424 PHOSPHATE CREAM. Patients who are non-responders, to physician choice standard of care, will undergo a washout period and will be enrolled in the study.

Multiple safety studies have been conducted with INCB018424 PHOSPHATE CREAM (see Safety) and a dose of 1.5% cream BID on up to 20% BSA is deemed safe. (Investigator's Brochure) The Within each cohort, the maximum reduction from baseline in the total psoriasis lesion assessment scores for the treated lesions was observed at the end of treatment (Day 28). (Investigator's Brochure) Therefore, we propose a single center, exploratory, open-label, single-arm design study of 12 patients. Treatment naïve and treatment refractory patients with LP will be treated with INCB018424 PHOSPHATE CREAM.

Individuals with LP involving less than 20% of the BSA will be eligible. Individuals must have 4 lesions at baseline, however, a minimum of 10 lesions is ideal, which are at least 5mm in diameter. 10 lesions are ideal as 2 lesions will be index lesions and 8 or more lesions will be selected from as responsive or non-responsive at 4 weeks. All lesions except for one index lesion will be treated and all lesions will be annotated, photographed, and scored. The rationale for a minimum of 8 lesions is based upon the assumption of a 50% response rate at 2 weeks. With 8 lesions, there would be a less than 1% chance that all 8 lesions would respond. Ideally, the 2 index lesions will be 10mm in diameter but this is not a requirement. Prior treatment will be allowed; however, a washout period of 2 weeks for topical and 4 weeks for systemic agents is required. At the washout period, individuals will undergo evaluation with a PGA, BSA calculation, and have the 2 largest, representative lesions selected for evaluation using a modified CAILS score lesion A- treatment index lesion and B-index control lesion. The determination of which lesion receives treatment and which is a control will be determined randomly. The additional lesions will be photographed, measured, scored, and recorded with Modified CAILS scores as well. The later calculations will be used for the determination of responsive and non-responsive lesions. Additional Pruritus measures using the NRS and Skindex-16 will be collected at that time.

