8.2 Statistical Methods

Descriptive Statistics

Sample Size Computation and Power Analysis:

The sample size for this pilot study is set at 12 subjects for logistical and financial reasons. This is similar in size to other exploratory studies and will provide adequate data for estimation purposes for planning future studies. With 12 subjects, the study is intended to be for estimation purposes only.

Statistical Analysis Plan:

Data Analysis - The statistical analysis will provide descriptive summary statistics for categorical and continuous outcomes. Categorical variables will be described by their count and proportion of occurrence while continuous, normally distributed variables will be described by their mean and standard deviation; and continuous, non-normally distributed variables will be described by their median and range. The paired or unpaired Wilcoxon tests will be used to quantify differences in numerical outcomes while the Fisher's exact test and the McNemar's or Bowker's tests will be used to quantify changes in categorical variables.

If missingness occurs at random a mixed model will be utilized to assess the change in the lesion over time. A sensitivity analysis will be performed using the last observation carried forward and the results will be compared to that of the mixed-model.

Effect sizes will be estimated for the appropriate statistical tests that will be used for group comparisons in future studies. This will enable more accurate power and sample size estimates moving forward.

Bioinformatic Analysis:

RNA-seq analysis: We will use our recently developed LinNorm program (<https://www.bioconductor.org/packages/release/bioc/html/Linnorm.html>) to process RNA-seq data and detect differentially expressed genes (DEGs) by comparing the RNA-seq profiles. We will first find DEG between responsive and non-responsive samples from the same individual by using paired or unpaired Wilcoxon rank-sum test (depending on how the samples are collected). We will then rank each gene in the DEGs based on the occurrence frequencies in all 12 subjects

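### Week 0–4 lesion-count change is named as a primary measure of efficacy but has no control; a fall from baseline should not be read as a drug effect

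*Combined protocol and SAP*

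**What the plan says.** The primary objective (section 3) opens: "To determine the efficacy of INCB018424 PHOSPHATE CREAM as measured by the change in Modified CAILS score". The same sentence adds the change in lesion count as a second measure. Section 4.4 repeats both, the second as "change in lesion count (week 0 and week 4").

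Section 4.1 describes the design: "This is a single center, exploratory, open-label, single-arm design study of 12 patients". Within each patient there is one untreated lesion: "All lesions except for one index lesion will be treated", and "The determination of which lesion receives treatment and which is a control will be determined randomly". That lesion is a control for the Modified CAILS score. It is not a control for the number of lesions on the body.

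On analysis, section 8.2 says "The paired or unpaired Wilcoxon tests will be used to quantify differences in numerical outcomes". It gives no reference value, significance level or success rule for the count. It also says "With 12 subjects, the study is intended to be for estimation purposes only". Sections 8.1 and 8.2 both say that effect sizes will be estimated to help plan group comparisons in later studies.

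On natural history, section 2.1 states: "Most cutaneous LP resolves within one to two years".

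**The concern.** A paired Wilcoxon test of week 4 against week 0 in one arm asks whether the count changed. It does not ask whether the cream changed it. The two questions coincide only if untreated counts would stay level for four weeks, and the protocol's own background gives reason to doubt that. The signed-rank test responds to small falls in the same direction across most subjects, whatever their cause.

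Two things are at stake. A fall in a primary measure could be reported as efficacy when part or all of it is spontaneous resolution. And any effect size taken from the before-after count would carry that drift into planning. The changes from week 0 in Pruritus NRS, Skindex-16 and BSA are uncontrolled in the same way.

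**Working it through.** **1. The plan's own figure.** Section 8.1 gives about 88 subjects for a single arm, effect size 0.3 and 80% power. ((1.960 + 0.842) / 0.3)² = 87.2, which rounds up to 88. This reproduces at a two-sided 5% level. The plan does not state a level, so I assume that one below. The 12 subjects do not come from this calculation; section 8.2 attributes them to logistics and finance.

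**2. Four-week clearing rate (assumed).** Section 2.1 gives no four-week or lesion-level rate. If a share s of lesions clears by T weeks at a constant rate, r = 1 − (1 − s)^(4/T):

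- half by 2 years: 1 − 0.5^(4/104) = 2.6%
- half by 1 year: 1 − 0.5^(4/52) = 5.2%
- 80% by 1 year: 1 − 0.2^(4/52) = 11.6%

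**3. What the test needs.** If all k non-zero changes are falls, the exact two-sided signed-rank p-value is 2/2^k. Five give 0.0625 and six give 0.031. So six of 12 subjects losing at least one lesion, with none gaining, is enough.

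**4. Closed form: inert cream, no new lesions, independent clearing.** With L lesions per subject, q = 1 − (1 − r)^L is the chance that a subject loses at least one. The chance of significance is P(X ≥ 6), X ~ Binomial(12, q). Eligibility (sections 4.1 and 5.1) is at least 4 lesions, ideally 10.

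| L | r = 2.6% | r = 5.2% | r = 11.6% |
|---|---|---|---|
| 4 | q 0.101: 0.1% | q 0.192: 1.6% | q 0.391: 31% |
| 10 | q 0.234: 4% | q 0.413: 37% | q 0.710: 97% |
| 20 | q 0.413: 37% | q 0.656: 92% | q 0.916: >99% |

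**5. Simulation: 10–30 lesions per subject.** Week-4 count = Binomial(baseline, 1 − r) + Poisson(baseline × r × f), where f is the fraction of cleared lesions replaced by new ones. The test is the exact signed-rank with zeros dropped. The last row needs no simulation: it is P(X ≥ 6) for X ~ Binomial(12, r).

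| Scenario | r = 2.6% | r = 5.2% | r = 11.6% |
|---|---|---|---|
| no new lesions, exact counts | 34% | 90% | 100% |
| no new lesions, 10% counting error | 8% | 17% | 62% |
| half replaced (f = 0.5), exact counts | 6% | 18% | 46% |
| fully replaced (f = 1), exact counts | 2% | 3% | 4% |
| each patient's disease clears all at once | <0.1% | <0.1% | 0.1% |

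In the exact-count rows with no or half replacement, essentially every rejection is a fall.

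**6. Drift in the estimate.** The expected proportional change in count is −r(1 − f). That is −2.6% to −11.6% with no new lesions, −1.3% to −5.8% with half replaced, and zero with full replacement. If disease clears patient by patient, the mean fall is still 2.6% to 11.6%, although the test then rarely reaches significance. Drift can therefore sit in the estimate even where the p-value is not inflated.

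**The case against.** The strongest reply is that the study claims little. It is declared exploratory, open-label and single-arm, section 8.2 limits it to estimation, and the other primary measure already has a randomised within-patient control. All of that is true, and it keeps this point modest. It does not dispose of it. Section 3 still calls the count a measure of efficacy, section 8.2 still names tests, and a before-after estimate contains drift whether or not a p-value is quoted.

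A reader might infer more than the documents support:

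- **That the plan formally tests the count against zero and will declare efficacy on the result.** It states no hypothesis, level or success rule for the count. The zero reference is inferred from a general sentence about Wilcoxon tests.
- **That natural history makes the zero null false.** Section 2.1 speaks of disease resolving over one to two years. New lesions may offset cleared ones. Washout of 2 or 4 weeks before baseline (section 4.1) could push untreated counts upward. Section 2.1 places hypertrophic disease among the longer-lasting forms, and section 5.2 does not list it as excluded.
- **That the lesion-count change will size the next trial.** Sections 8.1 and 8.2 do not say which outcome will supply the effect size.

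The objection is also right that the highest rates need many lesions, exact counting and no new lesions. Supplemental 1 allows counts to be estimated in extensively affected regions, so exact counting is least realistic where counts are highest.

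**Conclusion.** The point stands as a matter of attribution. Lesion-count change is an uncontrolled before-after measure presented as primary evidence of efficacy, and comparison with zero change does not isolate the drug.

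The size is uncertain. With 10–30 lesions per subject, the chance that an inert cream gives a significant change runs from about 34–100% (exact counts, no new lesions), through about 6–46% (half replaced), to no more than about 5% (full replacement, or clearing all at once within a patient). At the minimum of 4 lesions and no new ones it is 0.1% to 31%. All of this rests on assumed clearing rates, a constant hazard, an assumed two-sided 5% level and, except in the all-at-once case, independent lesions. The direction of untreated drift is not certain either, given washout. Upward drift would hide an effect instead of creating one, and the count would be no easier to interpret. The documents do not support the stronger statement that a false efficacy finding is likely.

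**What to change.** - In sections 4.4 and 8.2, describe lesion-count change, and the Pruritus NRS, Skindex-16 and BSA changes, as uncontrolled change over time. Report each with a confidence interval, and state that a Wilcoxon p-value against zero will not be read as efficacy. Align the wording of section 3.
- Rest the efficacy conclusion, and the effect size carried forward for planning group comparisons, on the within-patient difference in week 0–4 Modified CAILS change between the randomised treated and untreated index lesions. This removes shared drift, though not the effect of open-label scoring.
- A paired table of index-lesion clearance at week 4 may be added for description only. An exact McNemar test on it is not a useful remedy: with 12 pairs and 2.6–11.6% control clearance, its power is about 4–9% if 30% of treated lesions clear and 29–52% if 50% clear.
- Do not set clearance of the other treated lesions beside that of the control lesion. The index lesions are the two largest, so that comparison is confounded by size.
- The contrast depends on the control lesion staying untreated. Section 4.1 also says that treatment starts on all lesions, so the two statements must be reconciled.

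The cost is wording and, if wanted, one table; no new assessments are needed. The downside is that the lesion-count result supports a weaker claim.

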4.5 Secondary Study Endpoints

Change in Pruritus NRS, (week 0 to week 4, week 0 to week 8, weeks 4 to 8, weeks 8 to 12), Change in Skindex-16 (week 0 to week 4, weeks 4 to 8, weeks 8 to 12), Change in Physician Global Assessment (PGA) (week 0 to week 4, week 0 to week 8, weeks 4 to 8, weeks 8 to 12), Change in BSA (week 0 to week 4, week 0 to week 8, weeks 4 to 8, weeks 8 to 12), Change in Modified CAILS (week 0 to week 8, weeks 4 to 8, weeks 8 to 12).

4.6 Primary Safety Endpoints

A thorough baseline screening will be followed for all patients and is outlined in Table-2. A detailed list of the methods in which baseline screening will be performed is outlined in Supplemental 2. All blood draws and safety assessments must be performed prior to study treatment administration. Appropriate safety assessments (e.g., evaluation of AEs and SAEs) should be repeated after dosing with study treatment. A physical examination, including general appearance and vital signs, will be performed as indicated in Table-2. If indicated, based on medical history and/or symptoms, additional exams will be performed at the discretion of the investigator. If possible, the same member of the study site staff throughout the study will perform assessments for an individual subject. Information for all physical examinations will be included in the source documentation at the study site. Significant findings that are present prior to the subject signing informed consent will be included in the Medical History. Significant findings made after the signing of the informed consent, which meet the definition of an AE, must be recorded as an AE. Vital signs (blood pressure, pulse, height, weight) will be assessed at each physical examination as indicated in Table-2 (see Supplemental 2 for details on how to acquire vital signs). Whether action needs to be taken to address notable vital signs will be decided by the investigator, considering the overall status of the subject. Laboratory studies will be drawn as indicated in Table-2. Whether action needs to be taken to address notable laboratory values will be decided by the investigator, considering the overall status of the subject. Hematology assessments will be measured at all scheduled study visits specified in Table-2. Serum chemistry will be a comprehensive metabolic panel will be measured at all scheduled study visits specified in Table-2.

If the prohibited treatment is being used during the study for any indication, the subject must discontinue use of the prohibited treatment if he/she wishes to continue in the study. In case of undue safety risk for the subject, the subject should discontinue study treatment at the discretion of the investigator/qualified site staff. If the subject received a live virus vaccination during the study, the subject must discontinue study treatment.

4.7 Identification of Source Data

All data in the study will be captured in the case report forms including:

- Safety measures
- Efficacy measures
- Laboratory studies
- Vital Signs
- Exploratory measures

5 Subject Selection Enrollment and Withdrawal

5.1 Inclusion Criteria

Subjects eligible for inclusion in this study must fulfill **all** the following criteria:

- Subjects must be able to understand and comply with the requirements of the study and communicate with the investigator. Subjects must give written, signed, and dated informed consent before any study related activity is performed. When appropriate, a legal representative will sign the informed consent according to local laws and regulation
- Both men and women must be at least 18 years of age at the time of screening
- Subjects must have clinical and histological features of LP
- LP up to 20% of the BSA
- Subjects must have a minimum of 4 lesions, ideally 10 lesions of LP
- Subjects must have treatment naïve cutaneous LP or treatment refractory disease, as defined by failure of at least one established treatment for LP
 - Failure of prior therapy
 - Topical treatment
 - Systemic immunosuppressant
 - Oral metronidazole
 - Oral sulfasalazine
 - Oral retinoid

5.2 Exclusion Criteria

Subjects fulfilling **any** of the following criteria are not eligible for inclusion in this study. To ensure the recruitment of a representative sample of all eligible subjects, the investigator may apply no additional exclusions.

- On excluded therapies, not on a stable dose of a therapy, or incompletely washed out for a therapy (Table-1.)
- Known hypersensitivity to any component of INCB018424 PHOSPHATE CREAM
- Variants of LP deemed by the investigators to be inappropriate for INCB018424 PHOSPHATE CREAM including by not limited to:
 - Erosive LP
 - Intertriginous LP
 - Oral LP
 - Facial LP

- Drug-induced LP
- Vaginal LP
- LP involving greater than 20% BSA
- Pregnant or nursing (lactating) women (pregnancy is defined as the state of a female after conception and until the termination of gestation, confirmed by a positive human chorionic gonadotropin (hCG) laboratory test)
- Women of childbearing potential [Post-menopausal or not of child-bearing potential is defined by: 1 year of natural (spontaneous) amenorrhea or Surgical bilateral oophorectomy (with or without hysterectomy), total hysterectomy or tubal ligation at least 6 weeks ago. Oophorectomy alone must be confirmed by follow up hormone level assessment to be considered not of child-bearing potential, defined as all women physiologically capable of becoming pregnant, unless they are using basic methods of contraception which includes:
 - Total abstinence (Periodic abstinence and withdrawal are not acceptable methods of contraception)
 - Female sterilization (bilateral oophorectomy with or without hysterectomy), total hysterectomy, or tubal ligation at least 6 weeks before taking study treatment. Oophorectomy alone requires follow up hormone level assessment for fertility.
 - Male sterilization (at least 6 months prior to screening). The vasectomized male partner should be the sole partner for that subject.
 - Barrier methods of contraception: condom or occlusive cap.
 - Use of oral, injected or implanted hormonal methods of contraception or other forms or hormonal contraception that have complete efficacy (failure <1%). (The dose of the contraceptive should be stable for 3 months)
- Active ongoing inflammatory diseases of the skin other than LP that might confound the evaluation of the benefit of INCB018424 PHOSPHATE CREAM
- Underlying condition (including, but not limited to metabolic, hematologic, renal, hepatic, pulmonary, neurologic, endocrine, cardiac, infectious or gastrointestinal conditions) which, in the opinion of the investigator, significantly immunocompromised the subject and/or places the subject at unacceptable risk for receiving an immunomodulatory therapy
- Active systemic infections during the 2 weeks prior to randomization (common cold viruses not included) or any infection that reoccurs on a regular basis.
- Current severe progressive or uncontrolled disease which the investigator renders the subject unsuitable for the trial or puts the subject at increased risk

